9.2 Setting

All patients aged 2 years and above who have been enrolled with a primary care physician for at least 1 year and had their first prescription recorded in the database at least 1 year ago will be included.

The population included in THIN is representative of the UK as a whole in terms of age, sex and geographic distribution ([Bourke, Dattani et al. 2004](#); [Blak, Thompson et al. 2011](#)). THIN has been extensively validated for use in pharmacoepidemiology ([Lewis, Schinnar et al. 2007](#)), and has been used successfully in studies of bleeding risk ([Tata, Fortun et al. 2005](#); [Smeeth, Cook et al. 2006](#); [García Rodríguez and Barreales Tolosa 2007](#); [de Abajo and Garcia-Rodriguez 2008](#); [Massó González and García Rodríguez 2008](#); [Raine, Wong et al. 2009](#); [Cea Soriano and García Rodríguez 2010](#); [Gaist, Wallander et al. 2013](#); [Garcia-Rodriguez, Gaist et al. 2013](#)).

The enrolment period will start on the day after rivaroxaban receives first marketing authorization for the ‘treatment of DVT and long-term secondary prevention of recurrent DVT and PE’. End of enrolment will be 31 December 2017 and end of follow-up will be 31 December 2018. Interim reports will be provided for data collected 2 and 4 years after the date that rivaroxaban receives NICE approval for DVT treatment (see [Section 6](#) for detailed milestones).

To study outcomes of interest ([Section 8](#)) for patients receiving rivaroxaban and comparators for DVT/PE treatment, SPAF or ACS, the same source population will be used as in the drug utilization study.

9.3 Variables

9.3.1 Patient characteristics and drug utilization

The following variables, including risk factors/potential confounders for the outcomes under study, will be collected for comparison between the two cohorts:

- age and sex distribution at index date; 
- dose of index drug at index date and duration of treatment (including pack size); 
- diagnosis associated with the prescribing of the index drug; 
- proportion of patients defined as naïve, non-naïve, recent switchers and distant switchers; 

- type and duration of other anticoagulant use before the index date among the non-naïve group; ✓
- number of pregnant women at index date; ✓
- number of pregnancies after the index date; ✓
- use of specific prescribed medications both in the year before the index date and following the index date, confirming the ACS indication: antiplatelet drugs (low-dose acetylsalicylic acid, clopidogrel, dipyridamole, prasugrel, ticlopidine and ticagrelor); ✓
- use of other prescribed medications both in the year before the index date and following the index date: anticoagulants (including dabigatran etexilate and apixaban), antiarrhythmic drugs, antihypertensive drugs, statins, anti-diabetic agents, non-steroidal anti-inflammatory drugs, oral steroids, acid-suppressive drugs, disease-modifying anti-rheumatic drugs, antidepressants, antipsychotic drugs, oral contraceptives, hormone-replacement therapy, strong inhibitors of either cytochrome P450 3A4 or P-glycoprotein (e.g. the systemic azole antimycotics ketoconazole, itraconazole, voriconazole and posaconazole and the HIV-protease inhibitor ritonavir), strong CYP3A4 inducers (e.g. rifampicin, phenytoin, carbamazepine or phenobarbital) and fluconazole; ✓
- renal disease based on diagnoses, most recently recorded before the index date and in following the index date, with estimated glomerular filtration rate (eGFR) or creatinine clearance (CrCl) to be obtained where available; ✓
- comorbidity based on diagnoses most recently recorded before the index date and in following the index date, such as haemorrhagic disease, liver disease, pancreatic disease, cancer (including the presence of malignant neoplasm), cardiovascular disease, cardiovascular risk factors (hypertension, diabetes mellitus, hyperlipidaemia and obesity), peripheral arterial disease, respiratory disease (asthma and chronic obstructive pulmonary disease), rheumatoid arthritis, osteoarthritis, gastrointestinal disease (recent gastrointestinal ulceration [including peptic ulcer disease], gastritis and duodenitis, dyspepsia and gastroesophageal reflux disease), oesophageal varices, arteriovenous malformations, vascular aneurysms or major intraspinal or intracerebral vascular abnormalities, thyroid disease, surgical procedures (including PCI, CABG, and recent brain, ophthalmic or spinal surgery, where recorded), presence of a prosthetic heart valve (if recorded), alcohol-related disorders, ventricular arrhythmia, anaemia, and history of intracranial haemorrhage, urogenital bleeding and gastrointestinal bleeding; if possible, a CHADS score will be calculated based on the presence of congestive heart failure, hypertension, age, diabetes mellitus and prior stroke or transient ischaemic attack; also, where possible, a HAS-BLED score for major bleeding risk (hypertension, renal disease, liver disease, stroke history, prior major bleeding or predisposition to bleeding, age > 65, medication usage predisposing to bleeding, alcohol usage history, labile INR [if available]) will be calculated; ✓
- smoking status, body mass index (BMI) and Townsend score: most recently recorded before the index date and following the index date;
- healthcare utilization in the year prior to the index date (e.g. PCP visits, outpatient visits and hospital admissions). ✓

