- The prevention of stroke and systemic embolism in adult patients with non-valvular atrial fibrillation (stroke prevention in atrial fibrillation [SPAF]) with one or more risk factors, such as congestive heart failure, hypertension, age \geq 75 years, diabetes mellitus, prior stroke or transient ischaemic attack (20 mg rivaroxaban od).
- The prevention of venous thromboembolism (VTE) in adult patients undergoing elective hip or knee replacement surgery (recommended dose: 10 mg rivaroxaban od for 35 days following hip replacement surgery and 14 days following knee replacement surgery).
- Co-administered with acetylsalicylic acid (ASA) alone or with ASA plus clopidogrel or ticlopidine, for the prevention of atherothrombotic events in adult patients after an acute coronary syndrome (ACS) with elevated cardiac biomarkers (recommended dose 2.5 mg bid).

As is the case with other anticoagulants, clinical studies of rivaroxaban have identified haemorrhage as an important safety outcome ([Lassen, Ageno et al. 2008](#); [Turpie, Lassen et al. 2009](#)). A post-authorization safety study programme is planned for several European countries. This document summarizes the design of a population-based study to characterize new users of rivaroxaban, assess patterns of drug utilization, including adherence to label recommendations, and to assess the risk of bleeding associated with rivaroxaban treatment compared with the standard of care in routine clinical practice in the UK, for ACS, DVT/PE treatment and SPAF. For DVT/PE treatment and SPAF, standard of care is treatment with the most widely used vitamin K antagonist, warfarin, and for the secondary prevention of ACS, standard of care is antiplatelet drug(s) such as low-dose acetylsalicylic acid, clopidogrel, dipyridamole, prasugrel, ticlopidine and ticagrelor.

8 Research questions and objectives

This post-authorization study was designed to assess patterns of drug utilization and to quantify outcomes related to safety and effectiveness in new users of rivaroxaban compared with new users of standard of care.

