9.1 Study design

This study has a cohort design including nested case–control analyses.

Cohorts of first-time users of either rivaroxaban or comparators will be identified using the date of first prescription (index date) of the respective drug (index drug) (Figure 1).

A patient will be considered eligible to enter the study cohort as a first-time user of rivaroxaban or a first-time user of “standard of care” when he or she has a first prescription of the drug recorded during the enrolment period. In the UK, for VTE prevention, DVT/PE treatment and SPAF, standard of care is treatment with the most widely used vitamin K antagonist, warfarin, and for the secondary prevention of ACS, standard of care is antiplatelet drug(s) such as low-dose acetylsalicylic acid, clopidogrel, dipyridamole, prasugrel, ticlopidine and ticagrelor.

Patients who have any record of being prescribed their index drug prior to the enrolment period or who qualify as members of both cohorts on the same day, will be excluded. If a patient qualifies as first-time user of both rivaroxaban and “standard of care” comparison drug during the enrolment period, she/he will be assigned to the cohort of drug first prescribed during the enrolment period, with the date of this prescription being the index date.

Many patients with ACS have a history of ischaemic heart disease for which platelet inhibition is standard treatment, and thus exclusion of patients with prior use of platelet inhibitors risks excluding a majority of typical ACS patients. Therefore, those who have been using one or more platelet inhibitors will remain eligible to enter the study.

Standard of care for ACS patients is combination therapy, and as such cohort assignment will be based on first use of rivaroxaban (in combination with aspirin or clopidogrel, or multi-antiplatelet therapy), or use of aspirin and clopidogrel and/or other antiplatelet medications.

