9.5 Study Size

All patients enrolled in THIN and meeting the inclusion criteria will be included. The size of the population receiving rivaroxaban will be dependent on market uptake across the indications of interest (DVT/PE treatment, ACS and SPAF).

According to a preliminary sample size calculation, based on an incidence of haemorrhagic stroke in warfarin-treated patients of 5 per 1000 person-years, 12,000 rivaroxaban-treated patient-years and 48,000 warfarin-treated patient-years would be required to exclude a 50% increased risk of haemorrhagic stroke in rivaroxaban-treated patients compared with warfarin-treated patients with a power of 80%.

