9.7.2.1 Primary safety outcomes

Crude incidence rates will be estimated for each of the three primary adverse outcomes in both cohorts. Age- and sex-adjusted rate ratios with 95% CIs will be estimated for each of the three primary adverse outcomes comparing rivaroxaban with standard of care using Poisson regression analysis based on person–time contribution (current, recent and past use as defined in [Section 9.7.2](#)).

Where numbers and data permit, adjustment will be made for baseline medication and comorbidity variables described in the drug utilization section, including indication and history of adverse outcomes (referral or hospitalization for haemorrhagic stroke, gastrointestinal bleeding or urogenital bleeding recorded at any time before the index date).

If numbers of final cases permit, estimation of the relative risk among rivaroxaban users will be adjusted for known risk factors of the specific outcome using logistic regression models in nested case-control analyses.

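### In ACS, cohort entry is not anchored to the qualifying event and time since that event is neither a listed variable nor a model term, so the ACS rate ratios may be confounded by it, in a direction the protocol does not settle

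*Protocol*

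**What the plan says.** **Time zero.** Protocol section 9.1 sets the index date at the first prescription of the index drug, and 9.7.2 starts follow-up there. No rule ties the index date to the qualifying event or limits the gap between them.

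**ACS treatment.** Section 7 gives the licensed ACS use of rivaroxaban in a sentence that begins "Co-administered with acetylsalicylic acid (ASA) alone or with ASA plus clopidogrel or ticlopidine, for the prevention of atherothrombotic events in adult patients after an" and goes on to name ACS. Sections 7 and 9.1 name antiplatelet drugs as the ACS comparator. Section 9.1 assigns ACS patients by first use of rivaroxaban in combination with antiplatelets, or by use of antiplatelets. It adds that "those who have been using one or more platelet inhibitors will remain eligible to enter the study".

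**Variables.** Section 9.3.1 lists "diagnosis associated with the prescribing of the index drug". It does not list the date of that diagnosis or the interval to the index date. The nearest measure of earlier treatment time is "type and duration of other anticoagulant use before the index date among the non-naïve group", and 9.1 defines naïve and non-naïve status only for DVT/PE treatment and stroke prevention in atrial fibrillation.

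**Models.** The rate ratios are adjusted for age and sex. For the primary outcomes there is a further step, conditional on sufficient data: "adjustment will be made for baseline medication and comorbidity variables described in the drug utilization section, including indication". That step also covers earlier occurrence of the outcomes themselves. Sections 9.7.2.2 to 9.7.2.4 have the same conditional step without naming indication or history. Time since event is named in none of them.

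**The concern.** The two ACS index dates can mark different points in one course of treatment. A comparator patient may enter when antiplatelets are first prescribed. A rivaroxaban patient enters when a further drug is added to them, on the same day or later. If bleeding, procedures and recurrent infarction cluster soon after the event, cohorts that enter at different distances from it carry different shares of the high-risk period, whatever the drugs do.

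Adjusting for age and sex does not address this. Adjusting for indication says which event occurred, not how long ago. The ACS ratios for bleeding and for myocardial infarction are at stake: a difference in entry time could be read as a drug effect, and without the interval a reader could not tell whether the cohorts are aligned.

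**Working it through.** **1. The plan's own figure.** The only quantitative target is in section 9.5, "based on an incidence of haemorrhagic stroke in warfarin-treated patients of 5 per 1000 person-years", for which "12,000 rivaroxaban-treated patient-years and 48,000 warfarin-treated patient-years would be required". With a true ratio of 1, expected events are 12,000 × 0.005 = 60 and 48,000 × 0.005 = 240. The standard error of the log ratio is √(1/60 + 1/240) = 0.1443. Power to exclude 1.5 is Φ(ln 1.5 / 0.1443 − 1.96) = 80.2%, taking two-sided 0.05, which the protocol does not state. The figure reproduces, but it concerns warfarin and haemorrhagic stroke. It does not size the ACS comparison.

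**2. Does any listed variable measure the interval in ACS?**
- Diagnosis behind prescribing (9.3.1): identifies the event, gives no date.
- Naïve/switcher status (9.1) and duration of earlier anticoagulant use (9.3.1): the classes do not cover ACS.
- Antiplatelet use in the prior year, PCI/CABG where recorded, hospital admissions in the prior year (9.3.1): related to a recent event, but none measures time since it. Admissions are healthcare utilization, which the medication-and-comorbidity adjustment does not name.
- Nested case-control models (9.7.2.1): known risk factors, unnamed, and only if case numbers permit.
- Sensitivity analyses (9.7.2.7): concern onset and offset of drug action. The section also promises to account for biases recognised in the utilization data, but an interval that is not derived cannot be recognised there.

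**3. Illustration of size, on assumed inputs.** The protocol gives no early-risk multiplier, no distribution of entry times and no ACS follow-up time. Assume a true ratio of 1, an event rate h times baseline for the first 30 days after the event, follow-up of D days, and fractions f (rivaroxaban) and g (comparator) entering after day 30. The mean relative rate for an on-time entrant is m = (30h + D − 30)/D, and for a late entrant it is 1. Then

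observed ratio = [m − f(m − 1)] / [m − g(m − 1)].

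For h = 2, m = 395/365 = 1.082 at one year and 120/90 = 1.333 at 90 days. For h = 4, m = 455/365 = 1.247 and 180/90 = 2.

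| h | f | g | D = 365 | D = 90 |
|---|---|---|---|---|
| 2 | 0.25 | 0 | 0.98 | 0.94 |
| 4 | 0.50 | 0 | 0.90 | 0.75 |
| 4 | 1.00 | 0 | 0.80 | 0.50 |
| 4 | 0.50 | 0.50 | 1.00 | 1.00 |
| 4 | 0 | 0.50 | 1.11 | 1.33 |

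With g = 0, a wider assumed grid (early rate 1.5 to 5 times, early period 4 or 13 weeks, mean follow-up 26 to 104 weeks, f from 0.25 to 1) runs from 0.995 to 0.33. A mid-range case (2-fold, 13 weeks, f = 0.5, 52 weeks) is 1.125/1.25 = 0.90. The last two table rows show that the sign depends on f relative to g, and the protocol gives neither.

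**The case against.** **Later rivaroxaban entry is not guaranteed.** A reader might infer that, because rivaroxaban cannot precede the antiplatelets, the early high-risk weeks fall mainly in the comparator and the ACS ratios are biased in favour of rivaroxaban by design. The protocol does not support that. Starting no earlier than the antiplatelet is not the same as starting late after the event: patients already on platelet inhibitors stay eligible and could add rivaroxaban promptly. Nothing ties comparator entry to the event either, so comparators may also enter late. Read literally, the rules in 9.1 exclude a patient who qualifies for both cohorts on one day and place in the comparator cohort a patient who starts antiplatelets in the enrolment period and adds rivaroxaban afterwards, which is the very patient the inference needs in the rivaroxaban cohort. Section 9.9 also concedes that in-hospital prescriptions and early post-discharge events may be missed. All of this stands against a claim about direction. None of it aligns the cohorts.

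**DVT/PE.** A reader might extend the point there, since that indication covers both treatment and prevention of recurrence. That mix applies to both cohorts, no asymmetry between them is shown, and switcher status and earlier anticoagulant duration are collected. The extension is not made.

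**Model detail belongs in an analysis plan.** This is fair for the exact bands. But the protocol itself fixes time zero, the variable list and the adjustment set, and the gap follows from those choices.

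**Partial proxies exist.** They do, as set out in the working, and outcome history is in the conditional adjustment for the primary outcomes. None measures the interval.

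**Conclusion.** The point holds for ACS only, as an inexpensive improvement. As written, the plan compares ACS cohorts whose entry is not aligned on time since the qualifying event, does not list the variable that would show the misalignment, and names no model term that would adjust for it. The ACS rate ratios may therefore be confounded.

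Direction and size are not established. Later rivaroxaban entry is plausible because of its add-on role, but it is an inference. The ratios above rest wholly on assumed early risk, entry times and follow-up. The smallest case, 0.98 at one year, is negligible. The most extreme in the table, 0.50, needs a fourfold early rate, every rivaroxaban user entering late, every comparator on time and only 90 days of follow-up. They show that the bias could matter, not that it does.

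**What to change.** 1. In section 9.3.1, add the number of days from the qualifying ACS event to the index date, and report its distribution by cohort.
2. In section 9.7.2, for the ACS outcome comparisons, split person-time by time since the event (for example 0–30, 31–90 and over 90 days). Include these bands with age and sex in the ACS Poisson models, not only in the step that depends on numbers.
3. Keep patients whose event cannot be dated as a separate category, in line with 9.7.2.6. Restriction of both cohorts to a common maximum interval is at most a sensitivity analysis, because it discards patients.
4. Reconcile the first-drug and same-day rules in 9.1 with the ACS combination-therapy rule in the same section, so that it is clear which cohort a patient enters who takes antiplatelets and then, or on the same day, adds rivaroxaban.

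**Cost.** One derived variable and a few sentences. Section 9.4 says the indication can be ascertained by reviewing the clinical history, so the event date should usually be found in the same review. The early bands may hold few rivaroxaban users, giving imprecise estimates there, and some events will remain undatable.

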9.4 Data sources

The data source for this study will be The Health Improvement Network (THIN) database in the UK. THIN includes information on over 3 million patients (approximately 5% of the UK population) that is systematically recorded by participating PCPs as part of their routine patient care and is anonymized and sent to THIN for use in research projects. The computerized information includes demographics, details of PCP visits, referrals to specialists and hospital admissions (including diagnostic and treatment information), results of laboratory tests and a free-text section. Prescriptions issued by the PCP are recorded electronically and the indication can be ascertained by reviewing the patient's clinical history. The Read classification is used to code specific diagnoses as reasons for each consultation (O'Neil, Payne et al. 1995; Stuart-Buttle, Read et al. 1996), and a drug dictionary based on data from the MULTILEX classification is used to record prescriptions (First Data Bank 2014).

Recently, a number of practices included in THIN database have been linked to the HES database. HES is a data warehouse containing details of all admissions, outpatient appointments and Accident and Emergency attendances at NHS hospitals in England.

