9.7.2 Safety and effectiveness outcomes

The two cohorts (of first-time users of rivaroxaban and first-time users of comparators) will be followed up from the index date until 12 months after the end of the enrolment period for potential outcomes (safety and effectiveness). For each outcome, the first referral or hospitalization for that

outcome during the follow-up period will be identified. A separate follow-up will be performed for each of the outcomes.

Crude incidence rates will be estimated in both cohorts for DVT/PE treatment, SPAF and ACS. Incidence will be computed using the person–time contribution of the study cohorts, stratified into current, recent, past and non-use. Current use will refer to person–time up to 7 days after the end of supply of the index drug, recent use will refer to person–time up to 90 days after the end of current use, past use will include all person–time contribution after the end of recent use up to 1 year after the end of current use, non-use will include all remaining time person–time contribution after past-use until end of follow-up.

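### The ACS indication may be confirmed partly by antiplatelet prescriptions written after the index date, although follow-up for bleeding starts on that date

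*Protocol*

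**What the plan says.** Section 9.3.1 lists the variables collected to compare the cohorts. Its antiplatelet bullet reads "use of specific prescribed medications both in the year before the index date and following the index date, confirming the ACS indication". The next bullet, on all other medicines, has the same two time windows but gives them no confirming role. Separate bullets collect the dose at the index date and the "diagnosis associated with the prescribing of the index drug". Section 9.4 adds that "the indication can be ascertained by reviewing the patient's clinical history".

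For ACS, Section 9.1 states that "cohort assignment will be based on first use of rivaroxaban (in combination with aspirin or clopidogrel, or multi-antiplatelet therapy"), with no time window for the combination; the comparator side is "or use of aspirin and clopidogrel and/or other antiplatelet medications". Earlier antiplatelet users are kept: "those who have been using one or more platelet inhibitors will remain eligible to enter the study".

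For outcomes, Section 9.7.2 says that the cohorts "will be followed up from the index date until 12 months after the end of the enrolment period for potential outcomes", and that "Crude incidence rates will be estimated in both cohorts for DVT/PE treatment, SPAF and ACS". Section 8.1.2 names ACS among the three indications of the primary safety objective, and Section 9.7.2.1 lists indication as an adjustment variable where numbers permit.

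**The concern.** A stratum in which event rates are counted from the index date should be defined by what is known on that date. If a later prescription can confirm membership, a patient has to stay alive and on antiplatelet treatment long enough to receive it. Patients who bleed first, die first or have antiplatelets withdrawn after a bleed are the ones least likely to do so.

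The two cohorts are not placed alike. A comparator patient enters on an antiplatelet, so such a record usually exists at index. A rivaroxaban patient needs a separate antiplatelet record. If early events go unconfirmed mainly among rivaroxaban users, the rivaroxaban ACS rate is too low, which is the direction that would hide a harm. Section 9.7.1 provides an *other* indication category, but the outcome rates in Section 9.7.2 cover only DVT/PE treatment, SPAF and ACS. An unconfirmed patient placed in *other* would therefore drop out of the indication-specific outcome rates altogether.

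**Working it through.** **The protocol's own figure.** There is none for ACS. The only calculation (Section 9.5) concerns haemorrhagic stroke against warfarin. At 5 per 1000 person-years, 12,000 and 48,000 patient-years give 60 and 240 expected events. The standard error of the log rate ratio is √(1/60 + 1/240) = 0.1443. With a true ratio of 1 and a two-sided 5% level (assumed, as none is stated), power to exclude 1.5 is Φ(ln 1.5/0.1443 − 1.96) = 80.2%. The stated 80% reproduces and is not affected by this point.

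**Who could depend on a later prescription?**

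1. A patient with an ACS diagnosis linked to the prescription, a prior-year antiplatelet record or an antiplatelet prescribed on the index day can be identified at index. The dose at index also helps, since Section 7 lists 2.5 mg bid only for ACS.
2. Section 9.9 concedes that in-hospital starts may be missing from general practice notes and that over-the-counter use is poorly recorded. Section 9.1 says that many ACS patients, not all, have earlier ischaemic heart disease. A first-ACS patient started on antiplatelets in hospital may therefore have no primary care antiplatelet record until after the index date.
3. The protocol does not say how many patients fall under item 2, nor which source prevails when sources disagree.

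**Illustration; every input is assumed.** Let the true rate ratio be 1. Let *f* be the share of rivaroxaban ACS patients who can be confirmed only by a post-index prescription, *w* the days until that prescription, *T* the follow-up in days, and *m* the hazard before day *w* relative to afterwards. Suppose that events before day *w* are lost in share *f* of the rivaroxaban patients and that none are lost in the comparator. Events are rare, so the loss of person-time is ignored. Then

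observed ratio = 1 − f × m·w / (m·w + T − w).

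Example: T = 365, w = 28, m = 3 gives 84/(84 + 337) = 0.1995. With f = 0.5 the observed ratio is 1 − 0.5 × 0.1995 = 0.900.

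| T | w | m | f = 0.2 | f = 0.5 | f = 1 |
|---|---|---|---|---|---|
| 365 | 7 | 1 | 0.996 | 0.990 | 0.981 |
| 365 | 28 | 1 | 0.985 | 0.962 | 0.923 |
| 365 | 28 | 3 | 0.960 | 0.900 | 0.800 |
| 365 | 56 | 3 | 0.930 | 0.824 | 0.648 |
| 180 | 28 | 3 | 0.929 | 0.822 | 0.644 |

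With f = 0 the ratio is 1.000 in every row. The effect grows with a longer window or a shorter follow-up.

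**The case against.** The strongest reply is that the protocol contains no drop-out rule. The bullet sits in a list of descriptive variables, and nothing says that a patient without a later antiplatelet prescription leaves the ACS stratum. Indication has its own variable, clinical history can be reviewed, and prior antiplatelet users stay eligible. Confirming may mean no more than corroborating a diagnosis already made. The date limit of an indication algorithm could also be left to the analysis plan.

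Most of this stands, and it limits the point. Three stronger readings are tempting, and the documents do not support them:

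- *Post-index prescriptions are the sole confirmation.* The bullet names the prior year as well, and other sources exist.
- *The condition acts on one cohort only.* The bullet applies to both cohorts. Section 9.1 describes ACS standard of care as combination therapy, so a comparator patient who bleeds before a second agent is recorded might also go unconfirmed. An antiplatelet index drug does not by itself establish ACS.
- *A true ratio of 1.5 would be reported as about 1.35.* That is 1.5 × 0.900 and needs, for example, a threefold early hazard over 28 days and half the rivaroxaban patients dependent on a later record. Neither figure is in the protocol. Section 9.7.2 specifies crude rates by indication, and no ACS-only rate ratio is explicitly planned.

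The appeal to the analysis plan does not dispose of the point. The protocol is not merely silent on timing: it gives post-index prescriptions a role in establishing indication, a role that it does not give to the other medicines listed.

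**Conclusion.** The design point holds in a limited form. As written, the protocol lets information from after the start of follow-up help to define an outcome stratum, with an open-ended window and no rule for combining the two windows. Bias is possible, and it would probably favour rivaroxaban, because comparator patients usually have an antiplatelet record at index. It is not a stated consequence of the text.

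The protocol does not allow the bias to be sized. Under the assumptions above, with 365 days of follow-up, the rivaroxaban ACS rate would be about 0–8% too low for a constant hazard and a window of 7 to 28 days. It would be up to about 20% too low for a threefold early hazard over 28 days. Less favourable assumptions give more, and the bias is zero if the diagnosis, the dose at index or the prior-year record always identifies these patients. The case for change rests on a predictable direction and an easy remedy, not on a demonstrated large effect.

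**What to change.** Reword the antiplatelet bullet in Section 9.3.1 so that the ACS indication is assigned only from diagnoses, procedures and prescriptions dated up to and including the index date, by the same rule in both cohorts. State that antiplatelet use after the index date is kept solely as descriptive or time-varying co-medication and never decides indication or stratum. The combination wording in Section 9.1 should point to the same date limit.

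The cost is one changed bullet, a cross-reference and one date limit in the algorithm; no new data are needed. There is a small downside: a few patients whose antiplatelets were supplied only by the hospital must be classified from the diagnosis record or will fall in the *other* category.
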